1.0 INTRODUCTION

1.1 Scarring after Mohs Surgery

A common and significant risk and side effect of surgery is scarring. A major obstacle in wound healing is the tension caused by the surrounding muscles. Although surgeons can close a wound to minimize this tension, the repeated contraction of the surrounding muscles in every day movement put recurrent stress on the wound, prolonging the healing process. This can also lead to the formation of hypertrophic scars. Botulinum toxin is a protein produced by the bacterium *Clostridium botulinum*, and it is well known as a neurotoxin. It blocks neuromuscular transmission, thereby preventing the affected muscle group from contracting. It was postulated that the injection of a botulinum toxin into the surrounding area of a scar would decrease contraction and thereby improve wound healing and scarring. Since then, there have been several studies describing the benefit of using botulinum toxin A (BTX-A) in improving aesthetic outcomes in facial wounds. The use of BTX-A is becoming an increasing part of common practice to minimize scarring. To date, no such studies exist using abobotulinumtoxinA (aboBTX-A, Dysport) nor are there studies looking specifically at post-Mohs reconstruction for skin cancer removal. Mohs surgery is a specific technique of dermatologic surgery used to treat skin cancer. A specific study on the use of aboBTX-A prior to repair of skin cancer defects on the forehead would be valuable and may prove to facilitate this practice into more general use among skin cancer surgeons to help in optimizing scar appearance.

1.2 Investigational Agents

1.2.1 Dysport

Dysport (abobotulinumtoxinA) contains botulinum toxin A. It is a purified neurotoxin type A complex that is produced from fermentation of the bacterium *Clostridium botulinum* type A, Hall strain. Dysport is currently indicated for use in reducing glabellar lines and in cervical dystonia.

Dysport is supplied in single-use, sterile vials for intramuscular injection. Each vial contains 300 units of lyophilized abobotulinumtoxinA with 125mcg of human serum albumin and 2.5mg of lactose. Prior to use, it is reconstituted with 2.5 ml of sterile, bacteriostatic 0.9% sodium chloride solution. This yields a solution equivalent to 10 units per 0.08cc.

1.2.1.1 Mechanism of Action

Dysport inhibits release of the neurotransmitter, acetylcholine, from peripheral cholinergic nerve endings. Toxin activity occurs in the following sequence: Toxin heavy chain mediated binding to specific surface receptors on nerve endings, internalization of the toxin by receptor mediated endocytosis, pH-induced translocation of the toxin light chain to the cell cytosol and cleavage of SNAP25 leading to intracellular blockage of neurotransmitter exocytosis into the neuromuscular junction. This accounts for the therapeutic utility of the toxin in diseases characterized by excessive efferent activity in motor nerves. Recovery of transmission occurs gradually within 3 months as the neuromuscular junction recovers from SNAP25 cleavage and as new nerve endings are formed.

1.2.1.2 Summaries of and clinical significance of non-clinical and clinical studies

Please see below and the Dysport package insert for more information.

1.2.1.3 Non-clinical and Clinical Pharmacokinetics

Please see below and the Dysport package insert for more information.

1.2.1.4 Major route of Elimination

Please see below and the Dysport package insert for more information.

1.2.1.5 Safety Profile

Dysport is an acetylcholine release inhibitor and a neuromuscular blocking agent indicated for the temporary improvement in the appearance of moderate to severe glabellar lines associated with procerus and corrugator muscle

Contraindications: Dysport is contraindicated in individuals with any allergy to any component of the preparation, including milk allergy. It is also contraindicated if there is a current infection at the proposed injection site.

Pregnancy: Dysport is Pregnancy category C. *Dysport* produced embryo-fetal toxicity when given to pregnant rats at doses similar to or greater than the maximum recommended human dose (MRHD) of 1000 Units on a body weight (Units/kg) basis. In an embryo-fetal development study in which pregnant rats received intramuscular injections daily (2.2, 6.6, or 22 Units/kg on gestation days 6 through 17) or intermittently (44 Units/kg on gestation days 6 and 12 only) during organogenesis, increased early embryonic death was observed with both dosing schedules. The no-effect dose for embryo-fetal developmental toxicity was 2.2 Units/kg (one-tenth the MRHD on a body weight basis). Maternal toxicity was seen at 22 and 44 Units/kg. In a pre- and post-natal development study in which female rats received 6 weekly intramuscular injections (4.4, 11.1, 22.2, or 44 Units/kg) beginning on day 6 of gestation and continuing through parturition to weaning, an increase in stillbirths was observed at the highest dose, which was maternally toxic. The no-effect dose for pre- and post-natal developmental toxicity was 22.2 Units/kg (approximately equal to the MRHD on a body weight basis).

There are no adequate studies in pregnant women, and therefore, no one pregnant or that could possibly become pregnant will be enrolled in the study unless they use adequate contraception. It is unknown whether Dysport is excreted in human milk.

Dysport has not been shown to be associated with male-mediated fetal toxicity. The reproductive NOEL following intramuscular injection of 0, 4, 8, and 16 U/kg was 4 U/kg in male rats and 8 U/kg in female rats. Higher doses were associated with dose-dependent reductions in fertility in male rats (where limb weakness resulted in the inability to mate), and an altered estrous cycle in female rats. There were no adverse effects on the viability of the embryos. In clinical practice, male contraception is not required with Dysport administration.

1.2.1.6 Rationale for the Proposed starting doses and dose escalation scheme

Please see below.

1.2.1.7 Metabolism of Investigational study agent in humans and its potential for drug interactions.

Not applicable.

1.3 Pre-Clinical Data

Not applicable.

1.4 Clinical Data

Three double-blind, randomized, placebo-controlled, clinical studies have evaluated the efficacy of *Dysport* for use in the temporary improvement of the appearance of moderate to severe glabellar lines. These three studies enrolled healthy adults (ages 19–75) with glabellar lines of at least moderate severity at maximum frown. Subjects were excluded if they had marked ptosis, deep dermal scarring, or a substantial inability to lessen glabellar lines, even by physically spreading them apart. The subjects in these studies received either *Dysport* or placebo. The total dose was 50 units delivered in equally divided aliquots to specified injection sites. Additional endpoints for each of the studies were post-treatment glabellar line severity of none or mild with at least a 1-grade improvement from baseline for separate investigator and subject assessments at Day 30.

Investigators and subjects assessed efficacy at maximum frown by using a 4-point scale (none, mild, moderate, severe). Overall treatment success was defined as post-treatment glabellar line severity of none or mild with at least 2 grade improvements from Baseline for the combined investigator and subject assessments (composite assessment) on Day 30 (see Table 6). Additional endpoints for each of the studies were post-treatment glabellar line severity of none or mild with at least a 1 grade improvement from Baseline for the separate investigator and subject assessments on Day 30.

After completion of the randomized studies, subjects were offered participation in a two-year, open-label re-treatment study to assess the safety of multiple treatments.

Table 6. Treatment Success at Day 30 (None or Mild with at least 2 Grade Improvement from Baseline at Maximum Frown for the combined Investigator and Subject Assessments (Composite))

Study	2 Grade Improvement	
	Dysport n/N (%)	Placebo n/N (%)
GL-1	58/105 (55%)	0/53 (0%)
GL-2	37/71 (52%)	0/71 (0%)
GL-3	120/200 (60%)	0/100 (0%)

Treatment with *Dysport* reduced the severity of glabellar lines for up to four months.

Please see attached package insert for more information.

1.5 Clinical Pharmacokinetics of *Dysport*

Using currently available analytical technology, it is not possible to detect *Dysport* in the peripheral blood following intramuscular injection at the recommended doses.

1.6 Placebo: Sterile Bacteriostatic 0.9% sodium chloride solution

Sterile, bacteriostatic 0.9% sodium chloride solution will be used as the placebo agent since abobotulinumtoxinA is reconstituted with the same solution. An equivalent unit to volume ratio will be used (10 units per 0.08cc). i.e. if the patient would be receiving 30 units, 0.25cc of bacteriostatic 0.9% sodium chloride would be drawn. See Standard Reconstitution table below.

Standard Reconstitution Table

Mix 1 vial of Dysport (300 units) with 2.5cc’s of Bacteriostatic 0.9% Sodium Chloride Concentration = 10 units per 0.08cc.

Dysport	Volume
6 units	0.05cc
12 units	0.1cc
15 units	0.125cc
24 units	0.2cc
30 units	0.25cc
36 units	0.3cc
54 units	0.4cc
60 units	0.5cc

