9.0 PHARMACEUTICAL INFORMATION

A list of the adverse events and potential risks associated with the investigational or commercial agents administered in this study can be found in Section 8.0

Name of Agent	Dysport
Chemical Name:	abobotulinumtoxinA
Other Names:	Clostridium botulinum type toxin A toxin-haemagglutinin complex
Classification:	Prescription Medicine
Molecular Formula:	Botulinum toxin type A, the active ingredient in Dysport (abobotulinumtoxinA), is a purified neurotoxin type A complex produced by fermentation of the bacterium Clostridium botulinum type A, Hall Strain. It is purified from the culture supernatant by a series of precipitation, dialysis, and chromatography steps. The neurotoxin complex is composed of the neurotoxin, hemagglutinin proteins and non-toxin non-hemagglutinin protein.
Mode of Action:	Dysport inhibits release of the neurotransmitter, acetylcholine, from peripheral cholinergic nerve endings. Toxin activity occurs in the following sequence: Toxin heavy chain mediated binding to specific surface receptors on nerve endings, internalization of the toxin by receptor mediated endocytosis, pH-induced translocation of the toxin light chain to the cell cytosol and cleavage of SNAP25

leading to intracellular blockage of neurotransmitter exocytosis into the neuromuscular junction. This accounts for the therapeutic utility of the toxin in diseases characterized by excessive efferent activity in motor nerves.

Metabolism:	Using currently available analytical technology, it is not possible to detect Dysport in the peripheral blood following intramuscular injection at the recommended doses
Product description:	Dysport is supplied in a single-use, sterile vial for reconstitution intended for intramuscular injection. Each vial contains 300 Units of freeze-dried lyophilized abobotulinumtoxinA, 125 micrograms human serum albumin and 2.5 mg lactose. Box containing 1 vial—NDC 99207-500-30
Solution preparation:	Prior to use, it is reconstituted with 2.5 ml of sterile, bacteriostatic 0.9% sodium chloride solution. This yields a solution equivalent to 10 units per 0.08cc.
Storage requirements:	Dysport is stored under refrigeration at 2–8°C, protected from light.
Stability:	Not Applicable.
Route of administration:	Intramuscular injection into the desired muscle.

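### The 54-unit row of the Standard Reconstitution Table does not fit the stated dilution or any other row: 0.4 cc holds 48 units, and 54 units needs 0.45 cc

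*Combined protocol and SAP*

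**What the plan says.** Section 1.6 gives the preparation: "Mix 1 vial of Dysport (300 units) with 2.5cc’s of Bacteriostatic 0.9% Sodium Chloride Concentration = 10 units per 0.08cc". Section 1.2.1 gives the same vial content, diluent volume and ratio, and the Solution preparation entry in Section 9.0 repeats the diluent: "Prior to use, it is reconstituted with 2.5 ml of sterile, bacteriostatic 0.9% sodium chloride solution".

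Section 1.6 applies the same conversion to placebo ("An equivalent unit to volume ratio will be used (10 units per 0.08cc") and works one example: "if the patient would be receiving 30 units, 0.25cc of bacteriostatic 0.9% sodium chloride would be drawn". It then directs the reader to the Standard Reconstitution Table, which lists eight pairs of units and volume. The row in question is "54 units 0.4cc". It stands between "36 units 0.3cc" and "60 units 0.5cc".

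The dose is not fixed. Sections 1.7 and 6.1 leave the amount to the Mohs surgeon, up to 120 units, so 54 units is a permitted dose.

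**The concern.** The table can be seen to be irregular without knowing the concentration. From 36 to 54 units, a step of 18, the volume rises by 0.1 cc. From 54 to 60 units, a step of 6, it also rises by 0.1 cc. One fixed dilution cannot produce both steps.

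This is the only unit-to-volume table in the protocol, and Section 1.6 sends the reader to it. Section 3.2 allows up to five sites, and Section 9.0 has drug supplied directly to each, so it is the conversion reference that the sites share. Someone who uses this row to fill a 54-unit order draws the wrong volume. Someone who uses it in reverse, to turn a 0.4 cc draw into units, records the wrong dose. In either case the units recorded differ from the units given. Section 9.0 also requires accurate dispensing records and a final reconciliation of drug consumed, and unit entries taken from this row would carry the error into both.

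**Working it through.** **Inputs.** Vial content of 300 units, diluent volume of 2.5 cc, and the eight unit and volume pairs, all from Section 1.6. Sections 1.2.1 and 9.0 give the same vial content and diluent volume.

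**Concentration.** 300 / 2.5 = 120 units per cc.

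**Reproducing the plan's own example.** 30 units / 120 units per cc = 0.25 cc. This matches the worked placebo volume in Section 1.6, so 120 units per cc is the concentration the protocol itself uses.

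**Each row.** Implied concentration = units / volume. Units actually in the listed volume = volume × 120.

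| Units listed | Volume listed (cc) | Units per cc | Units in that volume at 120 per cc |
|---|---|---|---|
| 6 | 0.05 | 120 | 6 |
| 12 | 0.1 | 120 | 12 |
| 15 | 0.125 | 120 | 15 |
| 24 | 0.2 | 120 | 24 |
| 30 | 0.25 | 120 | 30 |
| 36 | 0.3 | 120 | 36 |
| **54** | **0.4** | **135** | **48** |
| 60 | 0.5 | 120 | 60 |

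Seven rows agree exactly and one does not.

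**Size of the discrepancy at 120 units per cc.**
- Volume needed for 54 units: 54 / 120 = 0.45 cc, which is 0.05 cc more than listed.
- Units in 0.4 cc: 0.4 × 120 = 48, which is 6 fewer than listed; 6 / 54 = 11.1%.
- If a 0.4 cc draw is recorded as 54 units, the record overstates the dose by 6 / 48 = 12.5%.

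**Does rounding of the stated ratio explain it?** The table header says "Concentration = 10 units per 0.08cc". At 120 units per cc, 10 units occupy 10 / 120 = 0.0833 cc, so 0.08 is a rounded figure. Taken literally, it means 10 / 0.08 = 125 units per cc. On that reading:
- 54 units would need 54 / 125 = 0.432 cc.
- 0.4 cc would hold 0.4 × 125 = 50 units, which is 4 short; 4 / 54 = 7.4%.

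The literal ratio therefore does not reproduce the row either. It would also put each of the other seven listed volumes about 4.2% too high (125 / 120 = 1.042), whereas the 54-unit volume is too low. The error runs the other way, so rounding is not its source.

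**The case against.** The arithmetic is not open to dispute. The case on the other side concerns consequence.

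- **The harm depends on use.** Someone has to draw or record from this row. The documents do not say how often that happens, or whether units or volume is the recorded field. This stands, and it limits the claim to syringes drawn from that row.
- **The table is not the only guide.** The ratio, the dilution and a correct worked example are also in the protocol. The table stops at 60 units while 120 are allowed, so larger doses need a calculation or a combination of rows in any case. This lowers the chance of error but does not remove it, since the text refers the reader to the table and 54 units is one of its eight entries.
- **Trial validity is largely untouched.** There is no fixed dose to violate. Sections 14.1.3 and 14.2 compare the arms on VAS and POSAS by Wilcoxon rank sum test without using dose. Placebo drawn from the same row has the same volume, so volume matching holds. All of this stands.
- **The direction is benign.** A 54-unit order filled at 0.4 cc is a small under-dose, well below the 120-unit ceiling, and so raises no overdose concern. This stands too.
- **The gap should be a range.** A literal reading of the rounded ratio gives 4 units rather than 6. The range is worth stating, but the dilution, the worked example and seven rows all support 120 units per cc, so 6 units is the better figure.
- **The row may be a PDF reading fault.** This cannot be excluded from text alone. However, the row is a complete pair in ascending order between two intact rows, and nothing suggests a lost digit or merged rows.

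These points limit the consequence. None of them reconciles the row with the rest of the protocol.

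**Conclusion.** The concern holds. The 54-unit row contradicts the stated dilution, the worked example and the other seven rows, and nothing elsewhere in the document corrects or explains it. The discrepancy is 6 units (11% of the listed dose) or 0.05 cc, taking 120 units per cc from 300 units in 2.5 cc. It is 4 units (7%) if the rounded ratio is read literally.

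The effect is confined to syringes drawn or recorded from this row. For active-arm patients, about 48 units would be given where 54 was ordered or recorded. The primary comparison, the sample size and volume-based blinding are not directly affected. The documents do not show whether the unit entry or the volume entry is the mistake. It should be corrected because it is a wrong figure in a drug-preparation table and is simple to put right.

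**What to change.** The sponsor should confirm which entry was intended and correct the row in one of two ways, either of which restores 120 units per cc:

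- 54 units in 0.45 cc, if the dose is the correct entry; or
- 48 units in 0.4 cc, if the volume is the correct entry.

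The corrected table should go to every site before syringes are drawn from it. If any have already been drawn, check the dispensing records for 54-unit or 0.4 cc entries and annotate the dose actually given.

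The change is one table cell and a notice to sites. Under Section 13.2.7 only the Coordinating Center may modify the protocol, and it handles the submission and approval of amendments, so the correction has to go through that route for up to five sites. It requires no change to the design, sample size or analysis.

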1.7 Rationale

The use of botulinum toxin A (BTX-A) induced chemoimmobilization of facial wounds to minimize scarring is becoming an increasing part of common practice. Several case reports and small clinical trials describe the benefit of using BTX-A in improving aesthetic outcomes in facial wounds.¹⁻⁵

The major factor impeding successful wound healing and therefore improved cosmesis is wound tension caused by surrounding muscles. Although surgeons can approximate wound edges to minimize this tension, repeated contractions of the surrounding muscle cause recurrent microtrauma. This prolongs the inflammatory response and increases localized metabolic activity, which can lead to hypertrophic scars.

A recent prospective clinical study evaluated the use of botulinum toxin A (Botox, Allergan, Irvine, CA) in improving facial wound healing found a statistically significant improvement in scar outcome compared with placebo.² No serious adverse events were reported.

To date, no such studies exist using abobotulinumtoxinA (aboBTX-A, Dysport) nor are there studies looking specifically at post-Mohs reconstruction for skin cancer removal.

A specific study on the use of aboBTX-A prior to repair of skin cancer defects on the forehead would be valuable and may prove to facilitate this practice into more general use among skin cancer surgeons to help in optimizing scar appearance.

In this study, each patient will be able to receive up to 120 units of Dysport/placebo at the initial visit to treat the entire forehead area (the frontalis, procerus, and corrugator muscles) to insure cosmetic symmetry. Toxin will be placed a minimum of 1.5cm above the orbital rim at the mid papillary line to minimize the risk of lid ptosis. The actual amount to be injected will be at the discretion of the Mohs surgeon based on his or her opinion of what amount is needed for sufficient wound paralysis and cosmetic symmetry. At the completion of the study, all subjects will be offered additional Dysport at no cost to the glabella as an on-label indication for improvement of glabella frown lines.

2.0 OBJECTIVES

To quantify the improvement in scar appearance, we propose the use of two well-established methods of measurement: The Visual Analogue Scale (VAS) and the Patient and Observer Scar Assessment Scale (POSAS)^{6,7} The VAS will be used as the primary end point. It consists of a 10 point scale to assess global scar assessment. Scar photographic images are assessed by independent physicians, and previous studies have shown very high intrarater consistency. The POSAS consists of two numeric scales. One scale is completed by the patients, the other by the clinician. This scale is different than previous scales because it takes the patient’s input into consideration. It has good internal consistency and interobserver reliability.^{8,9}

2.1 Primary Objective:

To evaluate the efficacy of using aboBTX-A to improve wound healing prior to Mohs micrographic surgery and reconstruction for skin cancer as measured by the Visual Analogue Scale (VAS) at 6 weeks post surgery.

[figure not shown]
2.2 Secondary Objective:

- To evaluate efficacy of using aboBTX-A to improve wound healing prior to Mohs micrographic surgery and reconstruction for skin cancer as measured by the Patient and Observer Assessment Scale (POSAS) at week 1, 6, and 24.
- To evaluate the efficacy of using aboBTX-A to improve wound healing prior to Mohs micrographic surgery and reconstruction for skin cancer as measured by the Visual Analogue Scale (VAS) at week 1 and 24 post surgery.
- To evaluate patient satisfaction
- To evaluate safety (adverse events)

3.0 STUDY DESIGN

3.1 Study Design including dose escalation/cohorts/subject numbers

This is a 6 month, prospective, multicenter, double-blinded, randomized, placebo-controlled study. A total of 40 male or female healthy volunteers, 20 in each arm, will be enrolled. Up to 10 more patients can be enrolled to account for patient drop-out. Subjects will all undergo Mohs micrographic surgical removal of a skin cancer lesion on the forehead followed by reconstruction. Subjects will be randomized to receive either aboBTX-A injection or placebo injection in the frontalis, procerus, and corrugator muscles prior to reconstruction. Photographs, POSAS, and clinical assessments will be taken immediately after initial wound closure, at 1 week follow-up, at 6 weeks follow-up, and at 6 months follow-up. Adverse events will also be reviewed at each study visit. After the completion of the study, the photographs will be assessed (blinded as to the patient identifiers) using a 10 cm visual analog scale (VAS). The first few photographs will be evaluated by the surgeons together to calibrate the VAS and ensure inter-reliability.

Procedure	Visit 1: Screening & Dysport Administration	Visit 2: Op Visit	Visit 3: 1 wk f/u	Visit 4: 6 wk f/u	Visit 5: 6 month f/u
Informed Consent	X				
Pre-op Evaluation	X				
Injection of Dysport or Placebo	X				
Adverse Events	X	X	X	X	X
Medical/Medication History	X	X	X	X	X
Photography	X	X	X	X	X
Skin Evaluation		X	X	X	X
Urine Pregnancy Test	X				X
Assessments					
Physician VAS				X	X
Patient POSAS		X	X	X	X
Physician POSAS		X	X	X	X
Patient survey					X

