3.4 Expected Duration of Subject Participation

3.4.1 Duration of Therapy

Study subjects will be given a one time treatment with Dysport at their first visit. This one time injection of Dysport is expected to cause an effect for approximately 3 months.

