11.0 STUDY PARAMETERS AND CALENDAR

11.1 Study Parameters

11.1.1.1 Screening Evaluation and Initial Visit (1 hr)

Screening studies and evaluations will be used to determine the eligibility of each subject for study inclusion. All evaluations must be completed ≤ 28 days prior to administration of protocol therapy.

- Informed consent: Prior to study initiation, each subject will be screened to ensure they meet all of the inclusion and none of the exclusion criteria outlined above. Potential subjects will be interviewed and examined by the investigator or his designee to establish their eligibility for inclusion in the study. Subjects will be given a full description of the nature and purpose of the study. If a subject is willing to participate, they must provide written informed consent before proceeding with the study.
- Inclusion and Exclusion criteria
- Demographics
- Medical History
- Pre-op evaluation by Mohs surgeon, which includes focal skin exam
- Vital signs including: blood pressure, pulse, respiratory rate
- Concomitant Medications Assessment including aminoglycoside, or other agents interfering with neuromuscular transmission (e.g., curare-like agents)
- Urine pregnancy test
- Randomization
- Injection of Dysport or placebo
- Review AEs
- This visit will take place 2-4 weeks prior to planned Mohs procedure, + or – 3 days
- Baseline photographs

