11.2 Treatment Period

Visits 2-5 can be scheduled +/- 5 days from indicated date.

Visit 2: Op Visit (30 minutes)

- Localized skin evaluation
- Vital signs including: blood pressure, pulse, respiratory rate
- Concomitant Medications Assessment including aminoglycoside, or other agents interfering with neuromuscular transmission (e.g., curare-like agents)
- Mohs procedure
- Reconstruction
- Photograph of wound before and after reconstruction
- POSAS

Patient and Observer Scar Assessment Scale (POSAS): The Patient and Observer Scar Assessment Scale (POSAS) consist of two numeric scales. One scale is completed by the patients, the other by the clinician. This scale is different than previous scales because it takes the patient's input into consideration. It has good internal consistency and interobserver reliability⁸⁻¹⁰. Patient POSAS will be collected at visit 2, 3, 4, and 5. Physician POSAS will be collected by each surgeon at visit 2, 3, 4, and 5. In addition, at the conclusion of the study, all four participating investigators will evaluate the photos of the wound at closure, at 6 weeks, and at 6 months for PSOAS scores in vascularity, pigmentation, thickness,

and surface area. Relief and pliability will not be assessed as photographs do not allow for measurement of these values.

- Review AEs, medical history, medications

Visit 3: 1 week follow-up (30 minutes)

- Localized skin evaluation
- Vital signs including: blood pressure, pulse, respiratory rate
- Concomitant Medications Assessment including aminoglycoside, or other agents interfering with neuromuscular transmission (e.g., curare-like agents)
- Suture removal
- Photograph of wound
- POSAS
- Review AEs, medical history, medications

Visit 4: 6 weeks follow-up (30 minutes)

- Localized skin evaluation
- Vital signs including: blood pressure, pulse, respiratory rate
- Concomitant Medications Assessment including aminoglycoside, or other agents interfering with neuromuscular transmission (e.g., curare-like agents)
- Photograph of wound
- POSAS
- Review AEs, medical history, medications

Visit 5: 6 months follow-up/End of study visit (45 minutes)

- Localized skin evaluation
- Vital signs including: blood pressure, pulse, respiratory rate
- Concomitant Medications Assessment including aminoglycoside, or other agents interfering with neuromuscular transmission (e.g., curare-like agents)
- Photograph of wound
- POSAS, VAS

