12.0 MEASUREMENT OF EFFECT

12.1 VAS: Visual Analog Scale. This is a 10 point scale to assess global scar assessment. At the conclusion of the study, photographs will be assessed in an independent and blinded fashion. After reviewing the photos of the wound at closure, at 6 weeks, and at 6 months, the participating raters will be asked to rate the cosmetic outcome at 6 weeks and 6 months on a 10-cm visual analog scale. The rater will be asked to assess the first patient together to establish a reference score for their respective further scores. Prior studies have shown very high intrarater consistency from VAS⁷. See statistical section for more information.

12.2 POSAS: Patient and Observer Scar Assessment Scale. The Patient and Observer Scar Assessment Scale (POSAS) consist of two numeric scales. One scale is completed by the patients, the other by the clinician. This scale is different than previous scales because it takes the patient's input into consideration. It has good internal consistency and interobserver reliability⁸⁻¹⁰. Patient POSAS will be collected at visit 2, 3, 4, and 5. Physician POSAS will be collected by each surgeon at visit 2, 3, 4, and 5. In addition, at the conclusion of the study, all four participating investigators will evaluate the photos of the wound at closure, at 6 weeks, and at 6 months for PSOAS scores in vascularity, pigmentation, thickness, and surface area. Relief and pliability will not be assessed as photographs do not allow for measurement of these values.

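### The primary 6-week scar photograph is taken while the forehead toxin is expected to be active, and no pose, framing or cropping is set to keep that from influencing the VAS

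*Combined protocol and SAP*

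**What the plan says.** - **Primary endpoint.** Section 2.1 assesses efficacy "as measured by the Visual Analogue Scale (VAS) at 6 weeks post surgery". Section 14.1.3 averages four physicians' scores and compares the arms with the Wilcoxon rank sum test.
- **Injection.** Section 11.1.1.1: "This visit will take place 2-4 weeks prior to planned Mohs procedure", with 3 days either way. The field is wider than the wound: section 1.7 gives the aim as "to treat the entire forehead area (the frontalis, procerus, and corrugator muscles) to insure cosmetic symmetry". Section 6.1 says the same.
- **Later visits.** Section 11.2: "Visits 2-5 can be scheduled +/- 5 days from indicated date".
- **Duration of effect.** Section 3.4.1: "This one time injection of Dysport is expected to cause an effect for approximately 3 months". Section 1.4 reports that treatment "reduced the severity of glabellar lines for up to four months".
- **Masking.** Section 3.1 calls the trial double-blinded and says "the photographs will be assessed (blinded as to the patient identifiers) using a 10 cm visual analog scale (VAS". Section 12.1 says "photographs will be assessed in an independent and blinded fashion". Neither section describes a method beyond hiding identifiers.
- **Images.** Sections 11.2, 12.1 and 13.2.2 describe photographs of the wound. No section sets facial expression, framing, cropping or the order in which patients are shown.
- **Rating sequence.** Under section 12.1 the raters look at the closure, 6-week and 6-month images and only then score 6 weeks and 6 months.
- **Raters.** Sections 2.0 and 14.0 call them independent physicians. Section 3.1 has the surgeons calibrate the scale together.

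**The concern.** The drug has a known cosmetic effect on forehead lines, and the primary endpoint is a global cosmetic score read from a photograph of treated forehead. Two separate routes lead to bias.

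The first is recognition. A rater who sees smooth skin or an altered brow next to the scar may guess the arm. Hiding names does not prevent this.

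The second needs no recognition. A rater who has no idea of the arm may still give a better global score because the skin around the scar looks smoother. Perfect concealment of allocation would not remove this route; limiting what is in frame would reduce both.

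The viewing sequence can strengthen either route, because the 6-month image shows the same forehead after the expected effect has ended. At stake is the meaning of a positive primary result: part of it could be the effect on lines rather than on the scar.

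**Working it through.** **1. Timing of the primary photograph.** Inputs: injection 14-28 days before surgery (11.1.1.1), photograph 42 days after surgery (2.1).

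- Nominal: 14 + 42 = 56 days to 28 + 42 = 70 days, or 8 to 10 weeks after injection.
- With the 3-day window at Visit 1 and the 5-day window at Visit 4: 11 + 37 = 48 days to 31 + 47 = 78 days, or 6.9 to 11.1 weeks.
- If the 5-day window at Visit 2 is stacked on top: 48 - 5 = 43 days to 78 + 5 = 83 days, or 6.1 to 11.9 weeks.

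All of these fall before about 13 weeks, the stated 3 months. The late image, taken as week 24 (2.2), falls at 14 + 168 = 182 to 28 + 168 = 196 days, or 26 to 28 weeks after injection. That is past both the 3-month and the four-month figures.

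**2. What each image can show.** The closure image is taken 2-4 weeks after injection and the 6-week image 8-10 weeks after, so both fall within the expected effect. Only the 6-month image falls outside it. A contrast between active and recovered forehead therefore becomes available when the 6-month image is shown beside the 6-week one, which is the sequence in section 12.1.

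**3. The plan's own figures.** Section 14.1.2 gives SDs of 1.4 and 2.2, and section 14.1.1 a minimal important difference of 1.5 points. 1.5/2.2 = 0.68 and 1.5/1.4 = 1.07, which reproduces the stated effect sizes of 0.7 to 1.1. The stated 80% power for effect size 1.0 with 20 per arm is conservative: the noncentral t gives 86.9%. This point does not rest on that figure; it borrows only n, SD and the 5% level from section 14.1.2. (Section 14.1.3 prints the threshold as 0.5, which is a separate matter.)

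**4. Sensitivity to a halo.** Assume no true scar effect and a shift of b points in the toxin arm from surrounding appearance. The documents give no value for b. With n = 20 per arm, df = 38 and noncentrality (b/SD) × √(20/2):

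| Halo b | SD | b/SD | Noncentrality | Two-sided rejection at 5% |
|---|---|---|---|---|
| 0 | either | 0 | 0 | 5.0% |
| 0.25 | 2.2 | 0.114 | 0.359 | 6.4% |
| 0.25 | 1.4 | 0.179 | 0.565 | 8.5% |
| 0.5 | 2.2 | 0.227 | 0.719 | 10.8% |
| 0.5 | 1.4 | 0.357 | 1.129 | 19.6% |

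Because the plan uses the Wilcoxon test, b = 0.5 was also simulated with normal scores (4,000 runs per case). Rejection was about 11% (SD 2.2) and 18% (SD 1.4), close to the table. Averaging four raters reduces their independent errors, but not a halo that all four share.

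**The case against.** The strongest reply is that the documents promise more masking than identifiers and may show less of the face than the concern supposes.

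- *A reader might infer that the ratings are blinded in no other respect.* The documents do not support that: section 12.1 says independent and blinded, sections 2.0 and 14.0 say independent physicians, and the trial is double-blinded. What stands is that no method is given for hiding appearance cues.
- *A reader might infer that any rater will see the missing lines or a changed brow.* The images are described as wound photographs, and no section says that the glabella, brows or opposite forehead are in frame. Equally, none says that they are not.
- *A reader might infer that an immobile forehead gives the arm away.* A still image shows smoothness, not immobility. The line data in section 1.4 were scored at maximum frown on Day 30, so they do not show how often a resting photograph at 8-10 weeks would reveal the arm. Section 1.2.1.1 describes gradual recovery within 3 months, so the effect may be waning by then.
- *A reader might infer that the trial cannot separate a scar effect from a line effect.* The 6-month VAS is a prespecified secondary endpoint, and a difference there could not come from lines still smoothed by the drug. It is only a partial check, because the same raters see all the images before scoring.
- *A reader might infer error rates far above those in the table.* A 1.0-point halo would give 29-60%, but it is two thirds of the minimal important difference and nothing in the documents supports it.

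Cropping also has limits. Section 4.1 admits lesions down to the eyebrow, so the brow cannot always be left out. Section 8.1.2 lists distortion of surrounding features as a surgical risk, and a tight crop could hide it.

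**Conclusion.** The point holds as a weakness in the protection of the primary endpoint, not as evidence that the trial is unblinded. The primary image falls within the expected drug effect under every reading of the visit windows, and the plan specifies nothing that keeps surrounding forehead out of the rating.

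Whether bias arises depends on what is in frame and on the expression, neither of which is stated. Its size cannot be derived from the documents. The rejection rates of about 6-9% and 11-20% are illustrations. They rest on an assumed halo of 0.25 or 0.5 points (one sixth or one third of the 1.5-point important difference), no true scar effect, 20 evaluable patients per arm, SD 2.2 to 1.4 and a 5% two-sided test. They show that a halo well below the important difference could matter at this sample size.

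The change is worth making because it is cheap and protects the primary endpoint.

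**What to change.** Amend sections 3.1, 11.2 and 12.1 as follows.

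1. Require a standard resting pose and standard framing for all photographs.
2. Before rating, crop every image to the scar plus a fixed margin, leaving out brows, glabella and the opposite forehead where the lesion site allows.
3. Remove site and date labels, and present patients in random order.
4. Score the 6-week image against the closure image before the 6-month image is shown; then score 6 months. This replaces the present sequence, in which all three are viewed first.
5. Have each photograph rater record a guess of the arm, and tabulate the guesses by arm.
6. Reconcile the statements that the raters are independent physicians (2.0, 14.0) and that the surgeons calibrate the scale (3.1). A treating surgeon may recognise a patient even from a cropped image.
7. Report the 6-month VAS beside the primary result as a supporting check.

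The cost is protocol wording, a processing step on existing digital files and one extra question per rated patient. Sample size, visits and treatment do not change. Rating takes place after the study is complete, so steps 2 to 5 can also be applied to photographs already taken. The downside is that raters lose some facial context for a global score, including any distortion outside the crop.
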